**NON-TECHNICAL ABSTRACT:**

Unfortunately, despite the best clinical efforts and breakthroughs in biotechnology, most patients diagnosed with advanced Stage melanoma continue to die from their disease. Reasons for this include: 1) patients are often diagnosed at a time when their melanoma has already spread to other sites such as the chest cavity, bone, liver, and brain limiting the options for surgical excision and 2) the cancer cells are resistant or become resistant to chemotherapy drugs used to treat the patient. Resistance to one type of chemotherapy agent often rapidly leads to resistance against many other chemotherapy drugs.

Harnessing the human immune system to target cancer could result in the development of effective treatment options against cancer and potentially enhance the effect of cytotoxic chemotherapy. Cancer cells produce a number of abnormal proteins or abnormal amounts of certain proteins found in normal cells. In some cancers, the abnormal protein expression may lead to an immune response against the cancer cells much in the same way the immune system responds to an infection. In progressive cancer however, the immune system fails to identify or respond to these abnormalities, and the cancer cells are not attacked or destroyed for reasons not yet fully understood.

From a practical standpoint, a successful tumor immunotherapy will likely require a combination treatment with additional therapeutic interventions that both activate an immune response and remove redundant mechanisms of tolerance maintenance. This clinical trial utilizes a combination of the two methods of cancer immunotherapy: the first, dorgenmeltucel-L, is intended to educate the human immune system to recognize the abnormal components found in melanoma cells, resulting in an immune response intended to destroy or block the growth of the cancer; and the second, a checkpoint inhibitor, will overcome tumor-induced immune suppression.

The investigational immunotherapy, dorgenmeltucel-L, helps the immune system of melanoma patients “identify” and target the cancerous tissue. This immunotherapy is engineered to mimic a key difference between human cells and the cells of other mammals. When a human immune system identifies cells or tissue labeled as “foreign” in this way, it “rejects” these cells or tissue. This “rejection” occurs when the patient’s immune system responds to differences between the cells of the transplanted organ and their own immune system by attacking the foreign tissue in the same way as it would attack infected tissue. This form of rejection is very rapid and highly destructive and the immunity it generates is long-lasting. This is called hyperacute rejection, and the immunotherapy used in this protocol tries to harness this response to teach a patient’s immune system to fight their melanoma just as the body would learn to reject a transplanted organ from an animal.

To achieve this hyperacute response, a mouse gene is placed into cultured human melanoma cells. These cells will express a molecule that will stimulate a strong immune response in humans. These cancer cells are irradiated to prevent any growth and then injected, along with the additional therapies, into patients with melanoma. The presence of the molecule will stimulate the patient’s immune system to kill the injected immunotherapy cells. As part of the process of destroying the immunotherapy cells, the patient’s immune system is stimulated to identify many differences between these cancer cells and normal human cells. This extra stimulation is thought to encourage immune responses against the melanoma in the patient based on shared abnormalities of the melanoma immunotherapy cells and the patient’s melanoma cells.

The standard of care agents used in this study, the checkpoint inhibitors of ipilimumab, nivolumab, or pembrolizumab, target mechanisms by which tumors evade a patient's immune system. Tumors acquire numerous potentially immune response provoking mutations as they develop. The immune system plays an important surveillance role in detecting and eliminating these malignant cells as they arise. This means that in order to grow, tumors must evade the host immune response. In essence, the host immune system must be rendered functionally tolerant to tumor-associated antigens. A phenomenon as complex as systemic tolerance requires that the tumor enlists the natural array of host regulatory pathways that already exist in the immune system.

In this protocol, patients with advanced melanoma will be given a checkpoint inhibitor (either ipilimumab, nivolumab, or pembrolizumab) with or without the dorgenmeltucel-L immunotherapy to assess the safety and progression-free survival (PFS) and overall survival (OS) rates in this patient population.

***PROTOCOL SYNOPSIS:***

Title: A Phase 2b Study of Immune Checkpoint Inhibition With or Without Dorgenmeltucel-L (HyperAcute Melanoma) Immunotherapy for Patients with Stage IV Melanoma

Primary Objectives: *Safety:* To determine the safety of administration of immune checkpoint inhibition with or without dorgenmeltucel-L (HyperAcute Melanoma (HAM)) immunotherapy for patients with Stage IV melanoma.

*Efficacy:* To assess the progression-free survival (PFS) of metastatic melanoma patients treated with immune checkpoint inhibition with or without dorgenmeltucel-L immunotherapy.

Secondary Objective: *Efficacy:* To assess the overall response rate, duration of response, duration of stable disease, and overall survival (OS) of patients with Stage IV melanoma treated with immune checkpoint inhibition with or without dorgenmeltucel-L immunotherapy.

*Biologic activity:* To measure possible anti-tumor immune responses in melanoma metastases in patients. To further determine whether the humoral and cellular mediated arms of the host immune system are activated secondary to dorgenmeltucel-L combined with immune checkpoint inhibition. Lastly, to perform correlative studies of patient blood samples (and tumor when available) to determine the mechanism of any observed anti-tumor effect.

Population: Patients with Stage IV metastatic melanoma  
**Arm 1:** Patients will receive immune checkpoint inhibition plus dorgenmeltucel-L  
Immune checkpoint inhibition consists of the treating physician's standard of care choice of ipilimumab, nivolumab, or pembrolizumab.  
**Arm 2:** Patients will receive immune checkpoint inhibition alone  
Immune checkpoint inhibition consists of treating physician's standard of care choice of ipilimumab, nivolumab, or pembrolizumab.

Sample Size: One hundred total patients will be randomized with equal allocation to Arm 1 (50 patients) and Arm 2 (50 patients). Patients will be stratified by immune checkpoint therapy and disease status and categorized as follows:

- 1) Immune checkpoint inhibition
- 2) Patients with unresectable advanced disease
- 3) Patients with resectable advanced disease who receive the immunotherapy in advance of resection

- 4) Patients with resected isolated advanced disease who are treated in a no apparent disease (NAD) state

Investigational Drugs:

Dorgenmeltucel-L (HyperAcute Melanoma) immunotherapy consisting of equal cell doses of each of three allogeneic melanoma cancer cell lines engineered to express the murine  $\alpha(1,3)$ galactosyltransferase gene.

Dosage Treatment:

Arm 1 will receive either:

Arm 1A - ipilimumab at 3 mg/kg given every 3 weeks x 4 doses **or**

Arm 1B - nivolumab at 240 mg given every 2 weeks **or**

Arm 1C - pembrolizumab at 2 mg/kg given every 3 weeks **AND** 300 Million HAM cells per each immunization, given every week x 4, every 2 weeks for 5 months, every month for 6 months, and every 3 months x 4;

Arm 2 will receive either:

Arm 2A - ipilimumab at 3 mg/kg given every 3 weeks x 4 **or**

Arm 2B - nivolumab at 240 mg given every 2 weeks **or**

Arm 2C - pembrolizumab at 2 mg/kg given every 3 weeks

Clinical Endpoints:

1. Safety
2. Progression-free survival (PFS)
3. Overall response rate
4. Duration of objective response
5. Duration of stable disease
6. Overall survival (OS)
7. ████████████████████

**Protocol Schemas for Arm 1A and Arm 2A**  
**Ipilimumab plus dorgenmeltucel-L - Arm 1A**  
**Ipilimumab Alone – Arm 2A**

Arm 1A: HAM + IPILIMUMAB			
Month	Week	Day	Treatment
	1	1	HAM
	2	8	HAM
	3	15	HAM
1	4	22	HAM + IPI
	5	29	REST
	6	36	HAM
	7	43	IPI
2	8	50	HAM
	9	57	REST
	10	64	HAM + IPI
	11	71	REST
3	12	78	HAM
	13	85	IPI
	14	92	HAM
	Evaluate for Response		
	15	99	REST
4	16	106	HAM
	17	113	REST
	18	120	HAM
	19	127	REST
5	20	134	HAM
	21	141	REST
	22	148	HAM
	23	155	REST
6	24		HAM
	Evaluate for Response		
7			HAM
8			HAM
9			HAM
	Evaluate for Response		
10			HAM
11			HAM
12			HAM
	Evaluate for Response		
15			HAM
	Evaluate for Response		
18			HAM
	Evaluate for Response		
21			HAM
	Evaluate for Response		
24			HAM
	Evaluate for Response		

Arm 2A: IPILIMUMAB ALONE		
Week	Day	Treatment
1	1	IPI
2	8	REST
3	15	REST
4	22	IPI
5	29	REST
6	36	REST
7	43	IPI
8	50	REST
9	57	REST
10	64	IPI
11	71	REST
12	78	REST
	Evaluate for Response	

IPI Alone Group: After treatment, observe for disease progression. If disease progresses, subjects go off study but will continue to be followed for survival status.

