### 3.2 *Eligibility and On-Study Tests*

Baseline and on-study tests will include (see Section 8.0 Study Calendar):

- Baseline history and complete physical examination
- Serum chemistries including electrolytes, BUN, creatinine, calcium, glucose and albumin; liver function tests including total bilirubin, ALT (SGPT) AST (SGOT), LDH, and alkaline phosphatase; quantitative immunoglobulins (IgG, IgM, and IgE); CBC with platelets and differential.

- Thyroid stimulating hormone (TSH) and free T4.
- Pregnancy testing with serum  $\beta$ -HCG in women of child-bearing potential
- Blood (approximately 16 mL) for measurement of anti-*agal* and anti-tumor antibodies to be drawn on Day 1 before treatment administration and as outlined in Section 8.
- For patients receiving the dorgenmeltucel-L immunotherapy, whole blood (approximately 10 mL) for replication competent retrovirus (RCR) testing on Day 1 prior to the first immunization and will be sent to NewLink Genetics.
- Contrast enhanced CT-scan of the chest and abdomen *or* whole body PET/CT fusion scan. CT-scan or MRI scan of the brain if known or suspected brain metastases. If indicated, CT scan of the neck, *or* ultrasound, PET-scan and/or radionuclide bone scan may also be obtained. PET scans and radionuclide bone scans may not be used for determination of response.
- Measurable disease or solid lesions, liver masses, lymph nodes and skin nodules will be measured and recorded pre-therapy using RECIST/irRC criteria.
- Whole blood (approximately 100 mL) in purple top tubes for PBLs for intracellular cytokines and ELISPOT to be drawn on Day 1 before treatment administration and as outlined in Section 8. These samples will be sent to NewLink Genetics for testing.

Baseline evaluations are to be conducted within 30 days prior to start of protocol therapy unless otherwise specified. In the event that the patient's condition has significantly deteriorated (e.g., significant increase in symptoms or worsening of ECOG PS), laboratory evaluations should be repeated within 5 days prior to initiation of therapy.

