### **Treatment must begin within 4-weeks of registration.**

Study Agent Administration (see **Appendix C**)

The dorgenmeltucel-L immunotherapy cells will be injected intradermally (i.d.) using tuberculin or other small syringe with a #25-gauge needle. Injections will be administered as divided doses and administered on an alternating basis with each immunotherapy cycle given in the upper and/or lower extremities. Immunizations will be avoided within an extremity that has previously undergone a complete lymph node dissection.

Patients will be monitored before and after each injection by the nursing staff.

- Monitoring is to include: temperature (T), pulse (P), blood pressure (BP) and respiratory rate (R), measured within 30 minutes before administration of the immunotherapy, and then within 30 minutes after the immunization. In addition, patients will be monitored for signs of acute allergic reactions including local or disseminated skin rash and other adverse reactions.
- Should an adverse event occur after discharge, patients will be instructed to immediately contact the Principal Investigator, Associate Investigator or research nurse for further evaluation and/or treatment.
- Patients developing Grade 2 or greater acute adverse reactions will be monitored for an additional 1-2 hours or until the AE has resolved to less than Grade 2. Medically indicated treatment of the AE will be administered. If an acute AE of Grade 2 or greater persists for more than 4-hours despite observation and/or treatment, a decision on whether to continue observation, institute or modify treatment of the AE, or admit the patient to the inpatient unit for further observation and/or treatment will be made by the Principal Investigators or designees.

A detailed description of the immunotherapy, storage, handling and reconstitution for immunization may be found in Section 6.1.

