### 8 STUDY CALENDARS

#### Study Calendar for Arm 1A (Ipilimumab plus Dorgenmeltucel-L Immunotherapy)

Ipilimumab 3 mg/kg IV given Q3 weeks x 4, dorgenmeltucel-L continues for up to 24 immunizations. Study visits may be performed +/- 3 days from the targeted study visit date to allow for holidays and other scheduling conflicts. Follow-up visits may be performed +/- 2 weeks from the targeted study visit date.

EVALUATIONS	Pre-Study DAY	Wk 1	Wk 2	Wk 3	Wk 4	Wk 5	Wk 6	Wk 7	Wk 8	Wk 9	Wk 10	Wk 11	Wk 12	Wk 13	Wk 14	Wk 16	Wk 18	Wk 20	Wk 22	Wk 24	Mo 7	Mo 8	Mo 9	Mo 10	Mo 11	Mo 12	Mo 15	Mo 18	Mo 21	Mo 24	1ST FUV						
HAM Injections		A	A	A	A		A		A		A		A		A	A	A	A	A	A	A	A	A	A	A	A	A	A	A	A	A						
Ipilimumab				X				X			X			X																							
Informed consent	X																																				
Demographics	X																																				
Medical history	X																																				
Concurrent meds	X																																				
Physical exam	X	X			X			X			X			X		X		X		X	-----Complete per SOC-----																X
Vital signs	X	X	X	X	X		X	X	X		X		X	X	X	X	X	X	X	X	X	X	X	X	X	X	X	X	X	X	X	X					
Height	X																																				
Weight	X	X			X			X			X			X		X		X		X	X	X	X	X	X	X	X	X	X	X	X	X					
Performance status	X	X			X			X			X			X		X		X		X	X	X	X	X	X	X	X	X	X	X	X	X					
CBC w/diff, plts	X	X			X			X			X			X		X		X		X	X	X	X	X	X	X	X	X	X	X	X	X					
Serum chemistry (with LDH)	B				B			B			B			B		B		B		B	B	B	B	B	B	B	B	B	B	B	B						
b-HCG	C																																				
TSH and Free T4	X				X			X			X			X																							
	E												E							E											E	E					
	F																																				
	H							H						H						H					H		H		H		H	H					
	I			I	I			I			I			I		I				I	I	I	I	I	I	I	I	I	I	I	I	I	I				
	J							J			J																										
Radiologic Tumor (RECIST/iRRC) evaluation	X													X						X			X			X	X	X	X	X	X	X					
AE/SAE Evaluation		-----Evaluate throughout Study and Follow Up Per Protocol-----																																			

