**Study Calendar for Arm 2B (Nivolumab Alone)**

Nivolumab 240 mg Q2 weeks until disease progression or significant toxicity Study visits may be performed +/- 3 days from the targeted study visit date to allow for holidays and other scheduling conflicts. Follow-up visits may be performed +/- 2 weeks from the targeted study visit date.

EVALUATIONS	Pre-Study	Wk 1	Wk 2	Wk 3	Wk 4	Wk 5	Wk 6	Wk 7	Wk 8	Wk 9	Wk 10	Wk 11	Wk 12	Wk 13	1ST FUV
		D1	D8	D15	D22	D29	D36	D43	D50	D57	D64	D71	D78	D85	
Nivolumab		X		X		X		X		X		X		X	
Informed consent	X														
Demographics	X														
Medical history	X														
Concurrent meds	X	X-----X													
Physical exam	X	X													X
Vital signs	X	X		X		X		X		X		X		X	X
Height	X														
Weight	X	X				X				X				X	X
Performance status	X	X		X		X		X		X		X		X	X
CBC w/diff, plts	X	X		X		X		X		X		X		X	X
Serum chemistry (with LDH)	B	B		B		B		B		B		B		B	C
B-HCG	C														
TSH and Free T4	X	X				X				X				X	
		E												E	E
		H						H							H
		I		I		I				I				I	I
		J						J				J			
Tumor measurements	X													X	X
Radiologic (RECIST/iRRc) evaluation	X													X	X
Adverse event evaluation		X-----X													X

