**Each Subsequent Cycle:**

- Pembrolizumab 2 mg/kg IV given every 3 weeks
- VS, PS, CBC, Chemistries, TSH and Free T4, [REDACTED] (monthly x 8, every 3 months x 4)
- Imaging for disease evaluation completed every 3 months

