**Follow Up Visits for ALL Subjects (after 1st FUV):**

- Imaging to be completed every 3 months until disease progression, after disease progression imaging is completed per standard of care
- Survival status checks to be completed at least every 3 months until death or lost to follow up
- All other assessments should be completed per standard of care practices.

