#### Other Reporting Requirements:

In addition to the clinical monitoring as outlined in the Study Calendars, monitoring for long-term or delayed adverse events related to gene transfer (required at least yearly for 15 years by the FDA-BRMAC) will be the responsibility of the Principal Investigator at each site. Each PI will be responsible for the recording and reporting of this information to the sponsor. Investigators must report the emergence of new clinical conditions, specifically:

- 1) New malignancy(ies);
- 2) New incidence or exacerbation of a pre-existing neurologic disorder;
- 3) New incidence or exacerbation of a prior rheumatologic or other autoimmune disorder;
- 4) New incidence of a hematologic disorder;
- 5) Unexpected illness and hospitalizations;
- 6) Expected or unexpected death and cause of death.

For the first 5 years, we recommend that Principal Investigators schedule a visit with each study subject to record new findings including history, physical examination, or laboratory testing at least once a year, even if the subject is off study. For the subsequent 10 years, we recommend that Investigators contact subjects by telephone or written questionnaire at least once a year to gather new information.

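### The protocol sets no common tumour-assessment dates across arms, so scan timing alone can bias the primary PFS log-rank test, in a direction the text leaves open

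*Combined protocol and SAP*

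**What the plan says.** **First assessment.** In the Protocol Schemas for Arms 1A, 1B and 1C, the first "Evaluate for Response" row stands between Week 14/Day 92 and Week 15/Day 99. In the schemas for Arms 2A, 2B and 2C it follows Week 12/Day 78, with no day of its own. In the Section 8 calendars, the Arm 1A row "Radiologic Tumor (RECIST/iRRC) evaluation" has its first on-study mark in what reads as Week 13. The control calendars (for Arm 2B, "Radiologic (RECIST/iRRc) evaluation") read Week 13/Day 85. In Arm 1C the mark reads as Week 12. It shares a column with the fourth pembrolizumab mark, which the schema puts at Week 13, so the row is probably shifted by one column.

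**Later assessments.** Arm 1 schemas and calendars give Week 24, then Months 9, 12, 15 and so on. Control has only an interval: "Imaging for disease evaluation completed every 3 months" in the text under the Arm 2C calendar, and "Imaging to be completed every 3 months until disease progression" in the follow-up text for all subjects. The interval line also appears under the Arm 1C calendar, beside its fixed dates. No starting point is given for counting the interval.

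**Which table governs.** Section 3.2 says "Baseline and on-study tests will include (see Section 8.0 Study Calendar" and lists CT and lesion measurement among those tests. Section 9.1 says only that every arm is assessed at roughly three-month intervals. No clause gives the calendars or the schemas precedence.

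**Time origin.** Section 12.3 does not state when PFS starts. Section 4.2 says "Treatment must begin within 4-weeks of registration", so randomisation and treatment Day 1 can differ by up to 28 days.

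**The concern.** RECIST progression is mostly seen at scans, so its recorded date depends on when the scan takes place. If one arm is scanned a week later than the other, progressions in that interval are recorded a week later in that arm, although nothing differs biologically. The log-rank test reads this as a treatment difference.

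The first scan matters most here, because Section 12.1 assumes a control median of 3 months and that is about when the first scan falls. The trial has 50 patients per arm and a two-sided type I error of 0.20, that is 0.10 in each direction. The two sets of tables therefore bear on the error rate of the primary efficacy test. A site can follow either set in good faith.

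**Working it through.** **1. The plan's own figure.** Section 12.1 asks for 96 events. By Freedman's formula, events = (z₀.₉₀ + z_power)² × [(1 + HR)/(1 − HR)]².

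- HR 0.6435, 80% power: (1.2816 + 0.8416)² × (1.6435/0.3565)² = 4.508 × 21.25 = 95.8, so 96.
- HR 0.6895, 70% power: (1.2816 + 0.5244)² × (1.6895/0.3105)² = 3.261 × 29.61 = 96.6, so 97.

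The stated 96 is reproduced for the first and is within one event for the second. The sample size is not in question.

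**2. Events exposed at the first scan.** With exponential PFS and a 3-month median (91.3 days), the share progressed by day d is 1 − 2^(−d/91.3). This gives 44.7% at Day 78, 47.5% at Day 85 and 50.3% at Day 92.

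**3. Where the later scans fall.** Week 24 is Day 162. The schemas label Month 1 as Week 4 and Month 6 as Week 24, so Months 9 and 12 may be four-week months (Week 36 = Day 246, Week 48 = Day 330) or calendar months (about Days 274 and 365). Control in three-month steps from Day 85 is scanned at about Days 176 and 268.

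- Second scan: Arm 1 is about 14 days earlier than control.
- Third scan: Arm 1 is about 22 days earlier with four-week months, or about 6 days later with calendar months.

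A later first scan in Arm 1 pushes the test toward the vaccine. Earlier later scans push it toward control. The net lean depends on both.

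**4. Simulation under no effect.** From the plan: 50 per arm, 3-month median, two-sided 0.20 (critical value 1.2816) and the ±3-day visit window. Assumed: exponential PFS, every patient followed to an event, progression dated at the next scan, an unstratified log-rank test, and 0% to 40% of events dated off schedule at their true time. The first number in each range is for 0% off schedule, the second for 40%.

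| First scan, Arm 1 v control | Later scans | Chance of a significant result (nominal 0.10) |
|---|---|---|
| Common dates | Common | About 0.10 each way |
| Day 92 v 85 | Common | 0.31 to 0.17 for vaccine |
| Day 92 v 85 | Arm 1 calendar months, control steps | 0.40 to 0.20 for vaccine |
| Day 92 v 85 | Arm 1 four-week months, control steps | 0.16 to 0.12 for vaccine |
| Day 92 v 78 | Arm 1 four-week months, control steps | About 0.11 for vaccine; no lean |
| Day 85 v 85 | Arm 1 four-week months, control steps | 0.25 to 0.15 for control |
| Day 85 v 85 | Arm 1 calendar months, control steps | 0.12 to 0.14 for vaccine |

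An independent rerun agreed with these within simulation error.

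**5. Sensitivity.** For Day 92 v 85 with common later scans, medians of 4.1 to 5.5 months (the pembrolizumab figures in Section 2.5) give 0.12 to 0.21 for the vaccine. If PFS runs from randomisation, scans run from Day 1 and treatment starts 0 to 28 days later (uniform, an assumption), the same case gives 0.14 to 0.18 at the 3-month median. Section 8 allows ±2 weeks at follow-up visits. Applying that to control's later scans alone gave 0.09 to 0.10, so window width by itself is not the driver.

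**The case against.** The strongest reply is that the text points to one answer. Section 3.2 sends imaging to Section 8, the legible calendars agree on about Week 13, and Section 9.1 covers every arm. The schemas are summaries, and their evaluation rows carry no day of their own. The evidence from the calendars is also imperfect. In the supplied text Arm 1A's first ipilimumab mark falls under Week 3 although its schema says Week 4, its imaging row has one mark too many, Arm 1C looks shifted, and no Arm 1B calendar appears. These may be faults of text extraction and are not held against the plan.

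Much of this stands. Section 3.2 does favour the calendars, and under them the first-scan gap largely disappears. But there is no precedence clause, the Arm 1 schemas still bracket the first evaluation between Days 92 and 99, and the calendars do not fix control's later dates.

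A reader might infer that the plan tilts the primary test toward the vaccine. The documents do not support that without conditions. It needs Arm 1 to follow its schema and, in addition, later scans on common dates or a calendar-month reading. With four-week months and control in three-month steps the lean is small or absent. The opposite comfort, that following the calendars makes the test unbiased, is not supported either: on one reading both arms start at Day 85 and the test leans to control.

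The model is also simpler than the plan. The planned test is stratified, patients with no apparent disease are enrolled, and Section 9.1 defers some suspected progressions for confirmation. The sizes are therefore illustrative. The mechanism does not depend on these details.

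**Conclusion.** The concern holds in this form: the documents do not set common assessment dates across arms, and that can bias the primary PFS test. The first Arm 1 assessment has two dates about a week apart, control's later assessments have no anchor, and the PFS origin is unstated.

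Under no effect, the readings left open give anything from no lean to 0.40 for the vaccine, or up to 0.25 for control, against a nominal 0.10. The direction cannot be determined from the text. The figures rest on exponential PFS, a 3-month median, progression dated at scans and an assumed off-schedule share of 0% to 40%. Longer medians and more off-schedule detection shrink the effect of the first-scan gap. Nothing here shows that bias has occurred. This should be fixed, with medium confidence because parts of the calendars are hard to read.

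**What to change.** Reconcile the schemas, Section 8 and Section 9.1 into one tumour-assessment calendar, with identical first and later time points in weeks or days, the same window and the same time origin in every arm. State that this calendar governs. Define PFS in Section 12.3 from the same origin. Point the Section 5.1 reference in the irSPD text of Section 9.1 to this calendar, since Section 5.1 holds no scan schedule.

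If patients have already been scanned on staggered dates, add an interval-censored log-rank-type test as a sensitivity analysis. In simulation of the staggered first-scan cases (Day 92 v 85 and Day 92 v 78) it brought the chance of favouring the vaccine to 0.10 to 0.12 with 20% to 40% of events off schedule, and to 0.11 to 0.14 with none.

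The cost is protocol wording. With common dates (simulated at Week 13), power stays at 0.79 to 0.80 for HR 0.6435 and 0.69 to 0.70 for HR 0.6895. The origin involves a trade-off. Counted from randomisation, some scans may not coincide with dosing visits: a Week 13 scan would fall between treatment Day 57 (85 − 28) and Day 85. Counted from Day 1, scans match visits, but the full analysis set includes all randomised patients and any who are never treated would have no Day 1, so a rule for them is needed.
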